5.1.2 Hypotheses and Statistical Methods for Secondary Objectives

5.1.2.1 Hypotheses

Efficacy

Superior efficacy hypotheses for the prevention of laboratory-confirmed influenza illness caused by any influenza A or B type using a more stringent margin threshold of [REDACTED] in subjects 6 months through 35 months of age (ie, the 1st secondary efficacy objective):

[REDACTED]
[REDACTED]

If all the above efficacy objectives are demonstrated, superior efficacy hypotheses for prevention of laboratory-confirmed influenza illness caused by viral strains similar to those contained in the vaccine in subjects 6 months through 35 months of age and the prevention of laboratory-confirmed influenza illness caused by any influenza A or B type in subjects 6 months through 23 months of age (ie, the 2nd and 3rd secondary efficacy objectives respectively):

$$H_0: rVE \leq 0\%$$

$$H_A: rVE > 0\%$$

Immunogenicity

If all of the above confirmatory efficacy objectives are demonstrated, a superiority testing approach will be used to compare post-vaccination GMTs and seroconversion rates between QIV-HD and QIV-SD groups for each strain using a one-sided test with Type I error rate of 0.025 following the individual hypotheses:

Superiority for GMTs:

$$H_0^s: \frac{GMT_{QIV-HD}^s}{GMT_{QIV-SD}^s} \leq 1 \Leftrightarrow \log_{10}(GMT_{QIV-HD}^s) - \log_{10}(GMT_{QIV-SD}^s) \leq 0$$
$$H_A^s: \frac{GMT_{QIV-HD}^s}{GMT_{QIV-SD}^s} > 1 \Leftrightarrow \log_{10}(GMT_{QIV-HD}^s) - \log_{10}(GMT_{QIV-SD}^s) > 0$$

Where: s is one strain in the quadrivalent quadrivalent influenza vaccine (A/H1N1-like strain, A/H3N2-like strain, B/Victoria lineage-like strain, and B/Yamagata lineage-like strain)

GMT_{QIV-HD} is the HAI GMT at 28 days after the last vaccination in QIV-HD group

GMT_{QIV-SD} is the HAI GMT at 28 days after the last vaccination in QIV-SD group

Superiority for seroconversion where s is the strain:

$$H_0^s: \pi_{QIV-HD}^s - \pi_{QIV-SD}^s \leq 0$$
$$H_A^s: \pi_{QIV-HD}^s - \pi_{QIV-SD}^s > 0$$

Where: s is one strain in the quadrivalent quadrivalent influenza vaccine (A/H1N1-like strain, A/H3N2-like strain, B/Victoria lineage-like strain, and B/Yamagata lineage-like stain)

π_{QIV-HD} is the seroconversion rate in QIV-HD group

π_{QIV-SD} is the seroconversion rate in QIV-SD group

5.1.2.2 Statistical Methods

Efficacy

If the primary objective is demonstrated, the secondary confirmatory objectives will be tested. A hierarchical testing combined with a graphical approach will be used to adjust the multiplicity of the 3 secondary confirmatory efficacy objectives, which prevents any inflation of the overall one-sided Type I error beyond 2.5%.

For the 1st secondary objective, a superiority test using a more stringent margin of [REDACTED]

[REDACTED] will be performed only after the primary objective is demonstrated. No multiplicity adjustment is needed, and the same nominal alpha levels for the primary objective being used in the interim analysis (ie, one-sided [REDACTED]) and in the final analysis (ie, one-sided [REDACTED] if the stopping rule for superior efficacy is not fulfilled at the interim analysis or one-sided 0.025 without adjustment if otherwise) will be used. The FASE will be used as the main analysis set and the same analysis on the PPASE will be performed as a sensitivity analysis.

Additional sensitivity analyses for the primary and 1st secondary objectives will be performed as follows using the same statistical method for the final analysis of the primary endpoint as detailed above:

- Excluding all siblings participating in the study to evaluate potential bias due to within-siblings flu contamination. For this, any subjects who had a sibling enrolled in this study will be excluded
- Considering the first ILI episode as defined in [Section 4.4.3](#) but occurring from the first dose for the primary endpoint on the PPASE and FASE respectively

At the time of the final analysis, if superiority for the 1st secondary objective is demonstrated, a graphical approach of Holm with full alpha-propagation will be applied to control alpha within the 2nd and 3rd secondary efficacy objectives. If one of the 2nd and 3rd objectives is claimed for efficacy using a two-sided 97.5% CI, then the other one will be tested using a two-sided 95% CI to assess superiority. QIV-HD will be considered as superior to QIV-SD if the lower bound of the CI for the corresponding rVE is > 0%. Estimation of rVE for these two secondary efficacy objectives will be the same as those described for the primary objective above in [Section 5.1.1.2](#). The FASE will be used as the main analysis set and the same analysis on the PPASE will be performed as a sensitivity analysis.

For the prevention of laboratory-confirmed influenza illness caused by viral strains similar to those contained in the vaccine in subjects 6 through 35 months of age, a secondary analysis using similarity based on genetic sequencing and an exploratory analysis using similarity based on antigenic similarity when available or genetic similarity otherwise will be performed.

For descriptive purposes, rVE and 95% CIs as calculated in [Section 5.1.1.2](#) will be produced for each vaccine group for the following ILIs occurring \geq 14 days after vaccination:

- laboratory-confirmed as positive for any influenza A or B type, in subjects according to their previous vaccination status
- laboratory-confirmed as positive for viral strains similar to those contained in the vaccine, in subjects according to their previous vaccination status
- laboratory-confirmed as positive for any influenza A or B type, and associated with AOM
- laboratory-confirmed as positive for viral strains similar to those contained in the vaccine, and associated with AOM
- laboratory-confirmed as positive for any influenza A or B type, and associated with ALRI
- laboratory-confirmed as positive for viral strains similar to those contained in the vaccine, and associated with ALRI
- PCR-confirmed as positive for any influenza A or B types
- PCR-confirmed as positive for viral strains similar to those contained in the vaccine
- culture-confirmed as positive for any influenza A or B types
- culture-confirmed as positive for viral strains similar to those contained in the vaccine
- laboratory-confirmed as positive for any influenza A or B type and associated with hospitalization
- laboratory-confirmed as positive for viral strains similar to those contained in the vaccine and associated with hospitalization

Immunogenicity

If the 3 secondary confirmatory efficacy objectives are demonstrated, superior immunogenicity will be considered. The ratios of HAI GMTs 28 days after last vaccination (D28/D56) will be obtained between vaccine groups with the two-sided 95% CIs calculated using normal approximation of log-transformed titers. The differences in the HAI seroconversion rates between vaccine groups will be computed along with the two-sided 95% CIs by the Wilson-Score method without continuity correction. If the superiority is demonstrated for post-vaccination GMTs and seroconversion rates for the 4 strains (ie, the two-sided 95% CIs all lie above 0), the immunogenicity of QIV-HD will be considered as superior to QIV-SD. The Full analysis set for immunogenicity (FASI) as defined in [Section 5.2.5](#) will be used as the main analysis set.

For descriptive purposes, the statistics presented on [Error! Reference source not found.](#) will be produced for each vaccine group. All immunogenicity endpoints for HAI, SN and anti-NA will be summarized for each vaccine strain with 95% CIs in the Immunogenicity Analysis Set (IAS) as defined in [Section 5.2.7](#) by season and by vaccine formulation if applicable.

The 95% CIs for the GMTs on D0 and 28 days after the last vaccination (D28/D56), and fold-rise as GM of Titers ratios (GMTRs) will be calculated using normal approximation of log-transformed titers.

The 95% CIs for the proportions (seroconversion rates and derived binary indicators) will be based on the Clopper-Pearson method.

Reverse cumulative distribution curves (RCDC) against each strain will be performed for baseline (D0) and post-vaccination immunogenicity (D28 or D56 as appropriate).

Subjects enrolled in both Season 1 and Season 3 (ie, the re-vaccination cohort) have 4 vaccine schedules: QIV-HD + QIV-HD, QIV-HD + QIV-SD, QIV-SD + QIV-HD and QIV-SD + QIV-SD. For re-vaccination response, immunogenicity endpoints based on HAI titers against the 4 strains used in Season 3 will be summarized descriptively in re-enrolled subjects in the Immunogenicity Subset in Season 3 (and by 4 vaccine schedules) and in subjects who are in the Immunogenicity Subset and only enrolled in Season 3 (and by each vaccine group).

Safety

Safety results will be described for each vaccine group with the statistics as presented on [Table 5.1](#).

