5.1.2 Justification of the Study Design

Justification for the age range and correlate of protection evaluation

Health authorities such as the US Food and Drug Administration and European Medicines Agency (EMA) have accepted non-inferior immunogenicity studies in support of licensure of new influenza vaccine. Non-inferior immunogenicity is demonstrated by comparing the new SD influenza vaccine to a licensed SD influenza vaccine, for which there are existing efficacy data, through HAI titers and seroconversion rates against the strains contained in the vaccines.

However, demonstrating superior immunogenicity for QIV-HD is not sufficient evidence for demonstrating superior efficacy, therefore a relative efficacy study needs to be conducted to demonstrate superior efficacy.

Table 5.1 shows that in the Phase II QHD04 study, children 6 through 35 months of age vaccinated with QIV-HD 60 µg HA/strain/dose had the highest HAI GMT ratios (post-vaccination GMTs of QIV-HD/QIV-SD) compared to the other 2 dose formulations evaluated (30 and 45 µg HA/strain/dose). Results of the seroneutralization assay also showed that the QIV-HD 60µg HA/strain/dose formulation generated the highest geometric mean fold rises than the other 2 QIV-HD dose formulations evaluated. Thus, the QIV-HD dose formulation of 60 µg HA/strain/dose was chosen to be evaluated in the Phase III QIV-HD studies in children.

Table 5.1: QHD04 study: HAI GMT ratios (QIV-HD/QIV-SD)

Strain	Children 6 months through 35 months of age					
	QIV-HD 30µg		QIV-HD 45µg		QIV-HD 60µg	
	GMT ratio	(95% CI)	GMT ratio	(95% CI)	GMT ratio	(95% CI)
A/H1N1	2.13	(0.83 ; 5.47)	1.75	(0.69 ; 4.38)	4.24	(2.05 ; 8.76)
A/H3N2	0.93	(0.40 ; 2.15)	1.49	(0.61 ; 3.60)	3.14	(1.53 ; 6.44)
B/Victoria	1.23	(0.58 ; 2.62)	1.38	(0.64 ; 2.98)	2.04	(1.10 ; 3.77)
B/Yamagata	1.10	(0.55 ; 2.22)	1.18	(0.55 ; 2.54)	1.92	(1.08 ; 3.41)

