If all of the above confirmatory efficacy objectives are demonstrated, a superiority testing approach will be used to compare post-vaccination GMTs and seroconversion rates between QIV-HD and QIV-SD groups for each strain using a one-sided test with Type I error rate of 0.025 following the individual hypotheses:

$$H_0^s : \frac{GMT_{QIV-HD}^s}{GMT_{QIV-SD}^s} \leq 1 \Leftrightarrow \log_{10}(GMT_{QIV-HD}^s) - \log_{10}(GMT_{QIV-SD}^s) \leq 0$$

$$H_A^s : \frac{GMT_{QIV-HD}^s}{GMT_{QIV-SD}^s} > 1 \Leftrightarrow \log_{10}(GMT_{QIV-HD}^s) - \log_{10}(GMT_{QIV-SD}^s) > 0$$

$$H_0^s : \pi_{QIV-HD}^s - \pi_{QIV-SD}^s \leq 0$$

$$H_A^s : \pi_{QIV-HD}^s - \pi_{QIV-SD}^s > 0$$

where s: strain

If superiority is demonstrated for post-vaccination GMTs and seroconversion rates for the 4 strains, the immunogenicity of QIV-HD will be considered as superior to QIV-SD. The Full analysis set for immunogenicity (FASI) will be used as the main analysis set.

Immunogenicity endpoints will be summarized for each vaccine strain with 95% CIs. The 95% CIs for the GMTs and GMT ratios (GMTRs) will be calculated using normal approximation of log-transformed titers. The 95% CIs for the proportions will be based on the Clopper-Pearson method. The ratios of GMTs will be obtained between groups with the 95% CIs calculated using normal approximation of log-transformed titers. The differences in the seroconversion rates between groups will be computed along with the two-sided 95% CIs by the Wilson-Score method without continuity correction. Additional parameters may be displayed as appropriate.

Reverse cumulative distribution curves against each strain will be performed for baseline (V01) and post-vaccination immunogenicity (D28 or D56 as appropriate).

Safety

Safety results will be described for each vaccine group. The main parameters will be described with 95% CI.

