The sample size needed for the assessment of the primary objective of the study is expected to be approximately █ subjects and may be adjusted based on the blinded number of cases in order to maintain the likelihood of achieving approximately █ evaluable influenza cases from the PPASE meeting the primary endpoint.

These required numbers of evaluable influenza cases would provide at least █ power at final analysis to conclude on the primary objective under the following assumptions:

- The true rVE of QIV-HD to QIV-SD is █
- An overall one-sided Type I error rate 0.025 (█ spent at interim and final analysis, respectively)
- The lower bound of the CI of rVE should be > 5%
- An allocation ratio of QIV-HD to QIV-SD of 1:1
- An overall influenza attack rate of █ for the occurrence of an influenza case in the QIV-SD group
- █ of enrolled subjects evaluable for the primary endpoint

Based on the same assumptions and using a █ threshold, the power for the first secondary objective at final analysis is expected at █ approximately.

For the assessment of the two other secondary confirmatory efficacy objectives, the assumptions will be similar to those for primary objective except

- The lower bound of the CI for the corresponding rVE will be superior to 0 %.
- The true rVE of QIV-HD to QIV-SD is █ for each subset (ie, subjects 6 through 35 months of age against similar strains and subjects 6 through 24 months of age against any strains)
- █ evaluable influenza cases (█ of total cases) from each subset

For each objective, a █ power will be achieved with a two-sided 97.5% CI and an █ power will be achieved with a two-sided 95% CI.

For the immunogenicity assessments:

Approximately █ subjects will be assessed for HAI immunogenicity in Season 1. Based on Phase II immunogenicity results and assuming █ of non-evaluable subjects, this provides approximately █ probability to obtain 95% CIs of ratios of GMTs and differences in seroconversion rates excluding equality for a given season (formulation).

13 Ethical and Legal Issues and Investigator / Sponsor Responsibilities

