- The true rVE of QIV-HD to QIV-SD is [REDACTED] for each subset (ie, subjects 6 through 35 months of age against similar strains and subjects 6 through 24 months of age against any strains)
- [REDACTED] evaluable influenza cases ([REDACTED] of total cases) from each subset

For each objective, a [REDACTED] power will be achieved with a two-sided 97.5% CI and an [REDACTED] power will be achieved with a two-sided 95% CI.

5.5.2 For the immunogenicity assessments:

Approximately [REDACTED] subjects will be assessed for HAI immunogenicity in Season 1. Based on Phase II immunogenicity results from QHD04 and assuming [REDACTED] of non-evaluable subjects, with [REDACTED] evaluable subjects ([REDACTED] in each vaccine group), the study will have an overall [REDACTED] power to demonstrate the superiority for both HAI GMTs and seroconversion rates comparing QIV-HD to QIV-SD for all 4 strains with 1:1 allocation ratio ([Table 5.4](#)). The superiority margin is defined as 1 for GMTR and 0 for seroconversion rates for all 4 strains. The adjustment for alpha is not needed as the superiority for immunogenicity is concluded only when the superiority is demonstrated in both HAI GMTs and seroconversion rates for all 4 strains.

Table 5.4: Power to demonstrate superiority for immunogenicity

Strain	Endpoint	Estimates		Power (%)
		Expected seroconversion rate in QIV-HD	Expected seroconversion rate in QIV-SD	
A/(H1N1)-like strain	Seroconversion rate			
A/(H3N2)-like strain	Seroconversion rate			
B/(Victoria lineage)-like strain	Seroconversion rate			
B/(Yamagata lineage)-like strain	Seroconversion rate			
		Expected GMT ratio (QIV-HD/QIV-SD)	Expected SD (log10 titer)	
A/(H1N1)-like strain	GMT			
A/(H3N2)-like strain	GMT			
B/(Victoria lineage)-like strain	GMT			
B/(Yamagata lineage)-like strain	GMT			
Overall power				

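### The SAP's success rule for immunogenicity superiority applies a CI threshold of 0 to GMT ratios, although its own null and margin for the ratio are 1

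*SAP*

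**What the plan says.** The confirmatory immunogenicity objective is tested after all confirmatory efficacy objectives have been met. It compares HAI GMTs and seroconversion rates for each of the four strains.

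- **SAP 5.1.2.1 (hypotheses).** Each comparison is a "one-sided test with Type I error rate of 0.025 following the individual hypotheses". The GMT null is a ratio of at most 1, printed with its equivalent of a log10 difference of at most 0. The seroconversion null is a difference of at most 0.
- **SAP 5.1.2.2 (methods).** The GMT quantity is a ratio: "The ratios of HAI GMTs 28 days after last vaccination (D28/D56) will be obtained between vaccine groups with the two-sided 95% CIs". The intervals use a normal approximation on log titers. For seroconversion, the quantity is the difference in rates with a Wilson-score interval. The decision rule then covers both: "If the superiority is demonstrated for post-vaccination GMTs and seroconversion rates for the 4 strains (ie, the two-sided 95% CIs all lie above 0".
- **SAP 5.5.2 (power).** "The superiority margin is defined as 1 for GMTR and 0 for seroconversion rates for all 4 strains".
- **Protocol 12.1.2.1.1.** The corresponding sentence has no numeric threshold: "If superiority is demonstrated for post-vaccination GMTs and seroconversion rates for the 4 strains, the immunogenicity of QIV-HD will be considered as superior to QIV-SD".
- **Protocol 12.5.** Power is expressed as the probability of "95% CIs of ratios of GMTs and differences in seroconversion rates excluding equality".

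**The concern.** Zero is the no-effect value for a difference; for a ratio it is 1. The methods paragraph names one ratio and one difference, then judges both against 0. A confidence interval for a ratio of geometric means cannot reach 0, so the rule as worded asks nothing of the GMT comparison.

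The protocol has no such threshold, so the 0 came in with the SAP. The parenthesis is also the SAP's only statement, in terms of confidence intervals, of when superior immunogenicity is declared, and it sits in the methods section that programmers and report authors follow.

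At stake is a confirmatory claim. SAP 5.5.2 justifies making no alpha adjustment on the ground that superiority must be shown in both GMTs and seroconversion for all four strains. Under the literal rule only the four seroconversion tests would constrain the claim, and GMT superiority would be asserted without being tested.

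**Working it through.** **Is there a plan figure to reproduce?** No. The number of subjects, expected GMT ratios, SDs and power for immunogenicity (SAP Table 5.4) are redacted. The margin is a definition, so the check is whether the stated thresholds agree.

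**Step 1. The statements side by side**

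| Place | GMT quantity | GMT threshold | Seroconversion threshold |
|---|---|---|---|
| SAP 5.1.2.1 | ratio, or log10 difference | 1, or 0 | 0 |
| SAP 5.1.2.2 | ratio | 0 | 0 |
| SAP 5.5.2 | ratio (GMTR) | 1 | 0 |
| Protocol 12.5 | ratio | equality, so 1 | equality, so 0 |

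The second row is the outlier. Its wording, "ie, the two-sided 95% CIs all lie above 0", matches the other rows only if the GMT interval is read on a scale the paragraph does not name.

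**Step 2. What each threshold tests**

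Let L be the lower 95% bound of the log10 GMT difference. The lower bound of the ratio is 10^L.

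- 10^L > 0 for every finite L, so ratio CI above 0 is always true.
- 10^L > 1 exactly when L > 0, because 10^0 = 1. So ratio CI above 1 and log10 CI above 0 are the same test.
- The normal quantile for a two-sided 5% level and for a one-sided 2.5% level is 1.96 in both cases, so the 95% CI matches the stated one-sided 0.025 test.

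**Step 3. The three readings on the sponsor's Phase II intervals (protocol Table 5.1, ages 6 through 35 months)**

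| Dose | Lower bounds of GMT ratio (H1N1, H3N2, B/Vic, B/Yam) | log10 of lower bounds | Ratio CI > 0 | Ratio CI > 1 | log10 CI > 0 |
|---|---|---|---|---|---|
| 30 µg | 0.83, 0.40, 0.58, 0.55 | -0.081, -0.398, -0.237, -0.260 | 4 of 4 | 0 of 4 | 0 of 4 |
| 45 µg | 0.69, 0.61, 0.64, 0.55 | -0.161, -0.215, -0.194, -0.260 | 4 of 4 | 0 of 4 | 0 of 4 |
| 60 µg | 2.05, 1.53, 1.10, 1.08 | 0.312, 0.185, 0.041, 0.033 | 4 of 4 | 4 of 4 | 4 of 4 |
| All | | | 12 of 12 | 4 of 12 | 4 of 12 |

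The clearest case is A/H3N2 at 30 µg, ratio 0.93 (0.40 to 2.15). It passes the literal rule with a point estimate below 1. On the log10 scale it is -0.03 (-0.40 to 0.33), which fails.

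These intervals are symmetric on the log scale: √(0.40 × 2.15) = 0.927 against the printed 0.93, while the arithmetic midpoint is (0.40 + 2.15) / 2 = 1.275. They were therefore computed on logs and reported as ratios, which is the form a report author would be reading.

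**Step 4. Rejection rates per strain, simulated**

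The t-based CI on log10 titers was simulated with 40,000 draws per scenario. Assumed inputs, because the real ones are redacted: 200 or 700 subjects per group and SD 0.5 or 0.8 log10.

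| True GMT ratio | Ratio CI > 0 | Ratio CI > 1 (same as log10 CI > 0) |
|---|---|---|
| 0.5 | 1.000 | 0.000 |
| 0.8 | 1.000 | 0.000 to 0.001 |
| 1.0 | 1.000 | 0.0248 to 0.0259 |

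A second run at a true ratio of 1, with 1,000,000 draws, 100, 500 or 1,000 per group and SD 0.5 or 0.7, gave 0.0249 to 0.0252 for both corrected wordings. The intended rule has its stated 0.025 level. The literal one passes every time, whatever sample size and SD are assumed.

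**The case against.** The best defence is that the scale can be recovered. SAP 5.1.2.1, immediately before the methods section, prints the log10 difference with threshold 0 as equivalent to the ratio with threshold 1. The interval is constructed on log titers, so 0 is correct for it before back-transformation. SAP 5.5.2 states the margin of 1 outright. A rule that can never fail is one that nobody implementing the written hypotheses would knowingly code. On this view the parenthesis is loose shorthand and needs only a copy-edit.

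The Phase II contrast can also be challenged. All eight intervals on which the readings differ come from the 30 and 45 µg formulations, which are not used in this trial. At 60 µg every reading gives the same verdict.

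Much of this stands. The intended test is identifiable and valid, and the Table 5.1 counts illustrate the rule rather than forecast this trial's result. It does not rescue the sentence, though. The methods paragraph names only the ratio and never a log difference. The opening of SAP section 5 says titer results are antilogged for presentation, and the protocol's own table shows GMT comparisons as ratios. For efficacy, SAP 5.1.2.2 gives both the quantity and its threshold (the rVE lower bound against 0%). A confirmatory immunogenicity rule should do the same and not depend on an unstated change of scale.

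**Conclusion.** The point holds. The worded decision rule in SAP 5.1.2.2 is wrong for the GMT quantity it names and conflicts with SAP 5.1.2.1 and 5.5.2. Read literally, it makes the GMT half of the confirmatory immunogenicity criterion vacuous.

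The practical effect is limited. The hypotheses and margin still define a valid one-sided 0.025 test. The objective comes last in the hierarchy, all four seroconversion comparisons must also succeed, and no efficacy claim depends on it. Alpha, sample size and power do not change. This is an error of wording in a confirmatory criterion, not a flaw in the planned test, and it should be fixed before unblinding.

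The conclusion rests on the text and on the fact that a back-transformed ratio is always positive. The assumed sample sizes and SDs in the simulation play no part in it.

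**What to change.** In SAP 5.1.2.2, replace the parenthesis with:

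> ie, for each of the 4 strains, the lower bound of the two-sided 95% CI is > 1 for the GMT ratio QIV-HD/QIV-SD (equivalently, > 0 for the log10 GMT difference) and > 0 for the seroconversion-rate difference

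This restores what SAP 5.1.2.1 and 5.5.2 already say and agrees with protocol 12.5. It costs one clause in the SAP, with no change to the protocol, alpha, sample size, power or data collection.
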